3.0 PATIENT ELIGIBILITY

3.1 Inclusion Criteria

3.1.1 Age \geq 18 years

- 3.1.2 For patients with *newly diagnosed disease*: diagnosis of "high-grade" MDS (≥10% blasts by morphology) or AML other than acute promyelocytic leukemia (APL) with t(15;17)(q22;q12) or variants according to the 2016 WHO classification. For patients with *relapsed/refractory disease*: prior diagnosis of "high-risk" MDS or non-APL AML, with relapsed/refractory disease according to 2003 recommendations of the International Working Group [21], requiring first or subsequent salvage therapy. Patients with mixed phenotype acute leukemia (MPAL) are eligible.
- **3.1.3** Outside diagnostic material is acceptable as long as peripheral blood and/or bone marrow slides are reviewed at the study institution. Flow cytometric analysis of peripheral blood and/or bone marrow should be performed according to institutional practice guidelines.
- **3.1.4** Patients with prior autologous or allogeneic hematopoietic cell transplantation (HCT) are eligible if relapse occurs provided symptoms of graft-versus host disease are well controlled with stable use of immunosuppressive agents.

- **3.1.5** Treatment-related mortality (TRM) score ≤ 9.2 as calculated with simplified model [22] (see Appendix A).
- **3.1.6** Should be off any active therapy for AML with the exception of hydroxyurea for at least 14 days prior to study registration unless patient has rapidly progressive disease, and all Grade 2-4 non-hematologic toxicities should have resolved.
- **3.1.7** May have previously received monotherapy with demethylating agents for MDS or AML or treatment with a mitoxantrone- or cladribine-based regimen for MDS or AML, including G-CLAM, but *not* demethylating agent as priming for or in combination with chemotherapy.
- **3.1.9** Patients with symptoms/signs of hyperleukocytosis or WBC >100,000/ μ L can be treated with leukapheresis or may receive up to 2 doses of cytarabine (up to 500 mg/m²/dose) prior to enrollment.
- **3.1.10** Adequate organ function.

3.1.10.1 Bilirubin ≤ 2.5 x Institutional Upper Limit of Normal (IULN) unless elevation is thought to be due to hepatic infiltration by AML, Gilbert's syndrome, or hemolysis (assessed within 14 days prior to registration).

3.1.10.2 Serum creatinine $\leq 2.0 \text{ mg/dL}$ (assessed within 14 days prior to registration).

3.1.10.3 Left ventricular ejection fraction $\geq 45\%$, assessed within 3 months prior to registration, e.g. by MUGA scan or echocardiography, or other appropriate diagnostic modality and no clinical evidence of congestive heart failure. If the patient had anthracycline-based therapy since the most recent cardiac assessment, cardiac evaluation should be repeated if there is clinical or radiographic suspicion of cardiac dysfunction, or if the previous cardiac assessment was abnormal.

- **3.1.11** Women of childbearing potential and men must agree to use adequate contraception.
- **3.1.12** Ability to understand and willingness to sign a written consent.

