days of treatment initiation from thrombocytopenia-related intracranial hemorrhage. Overall, 29/31 patients (93.5%) achieved a CR, including 24 (77.4%) with complete count recovery, with 1-2 cycles of chemotherapy. One DLT occurred at each of dose levels 3 and 4 (respiratory failure in both cases), establishing 18 mg/m²/day as the MTD of mitoxantrone. Besides infections and neutropenic fever, maculopapular rash, nausea, and hypoxia were the most common grade 3+ adverse events. There were 26 relapsed and refractory patients treated in Phase 1 with median age 57 (37-77) years, median TRM score of 1.73 (range: 0.29-3.92). 2 patients died within 28 days of treatment initiation from sepsis and cardiogenic shock respectively. Overall, 13/36 patients (50%) achieved a CR, including 8 (31%) with complete count recovery. One DLT occurred at dose level 1 (nausea) and 2 at dose level 4 (encephalitis and cardiogenic shock), establishing 16 mg/m²/day as the MTD of mitoxantrone. Besides infections and neutropenic fever, the most common grade 3+ adverse events were nausea, hypoxia (fluid overload and infection related), and maculopapular rash.[20] The final results from the phase 1/2 study in newly-diagnosed patients were submitted in abstract form to ASH this year; similar rates of response and adverse events were reported.

PROTOCOL UPDATE (2-2018)

Rationale for restricting enrollment to newly diagnosed (ND) patients

Analysis of treatment outcomes for relapsed/refractory (RR) patients enrolled in this protocol revealed an increased rate of delayed blood count recovery (MLFS) over what would be expected based on experience with GCLAM without decitabine. Based on these cases, revisions to the RR arm of this protocol are being discussed. These revisions are beyond the scope of what can be accomplished with a protocol modification, and so we have elected to restrict this protocol to ND patients and to work on a new protocol for RR patients.

Rationale for allowing only 1 cycle of decitabine + GCLAM

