This protocol initially called for multiple cycles of decitabine in combination with chemotherapy: patients who failed to achieve CR without measurable residual disease (MRD), or MRDneg CR, were eligible for a 2nd cycle of decitabine + GCLAM, while those who did achieve this outcome were eligible for consolidation with decitabine + GCLA. Review of outcomes from the 4 ND patients who received on-protocol consolidation showed that 2 had delayed or absent recovery of neutrophils and platelets not related to leukemia, or morphological leukemia-free state (MLFS). Although it is difficult to interpret results from so few patients, in light of results from RR patients showing higher rates of MLFS than we would normally expect, we opt to restrict patients to a single cycle of decitabine in combination with GCLAM. Patients achieving MRDneg CR have the option of receiving GCLA consolidation (which is a standard therapy that they could receive on or off protocol), while those who do not achieve MRDneg CR will be taken off study. Because we recognize MLFS as a concern with this regimen, we will add criteria to the stopping rules to include bone marrow aplasia.

Rationale for adding a Phase 2 expansion cohort

Based on the 6 ND patients who have had their responses assessed, the combination of decitabine for 10 days and GCLAM appears to be effective. Within our first cohort of 6 patients, we had 1 DLT (a patient experienced early death), but responses in the other 5 patients showed MRDneg CR. Without an expansion cohort, we only have room to enroll another 4 patients on

Protocol 9713.00

the trial to determine the MTD or recommended Phase 2 dose (RP2D) assuming that the remaining patients have only 0 or 1 DLT. Because of these promising early results, we plan to expand our study in ND patients at the MTD/RP2D. The Phase 2 expansion includes stopping rules for both efficacy and safety.

2.0 **OBJECTIVES**

2.1 Primary Objective

- **2.1.1** Estimate the maximum tolerated dose (MTD) of decitabine when used concomitantly with G-CLAM in patients with newly diagnosed AML and highrisk MDS.
- **2.1.2** Compare, within the limits of a phase 1/2 study, the rate of complete remission without measurable residual disease (MRDneg CR) with decitabine + G-CLAM at the MTD compared to similar patients treated previously with G-CLAM alone.

2.2 Secondary Objectives

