- 2.2.1 Evaluate, within the limits of a phase 1/2 study, disease response (complete remission, overall response rate) relapse-free survival (RFS), event-free survival (EFS), and overall survival (OS) in patients with newly-diagnosed AML / high-risk MDS.
- **2.2.2** Describe, within the limits of a phase 1/2 study, the toxicity profile of the study regimen.

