5.0 PROTOCOL REGISTRATION

To register, the attending physician involved in the care of the potential study participant must contact either the Principal Investigator or, in her absence, a PI-designated member of the study team, and fax a copy of the signed consent form and a signed HIPAA authorization form to the study team ([contact]). The study PI will be responsible for ensuring that all eligibility requirements according to section 3.0 are met. To complete the registration process, the Principal Investigator or his or her designee will assign a patient study number and register the patient on the study. A complete, signed study consent and HIPAA consent are required for registration.

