6.0 TREATMENT PLAN

This study is a single-center, open-label phase 1/2 study of decitabine given concomitantly with G-CLAM chemotherapy in adults with newly diagnosed AML or high-risk MDS. Since prior studies have suggested that the hypomethylating activity of decitabine plateaus at 20 mg/m²/d [23] and since data from Fred Hutch #2652.00 discussed above show that decitabine can be given safely for 10 days prior to intensive chemotherapy, we will start our trial with 10 days of decitabine at 20 mg/m²/d and will de-escalate the dose based on DLTs. We will use G-CLAM dose established based on data from Fred Hutch #2734.00 described above. Bone marrows will be reassessed upon blood count recovery or between day Days +25 to +35 after start of G-CLAM chemotherapy, whichever occurs first. Patients achieving CR or CR with incomplete neutrophil or platelet count recovery (CRi) after one induction course are eligible for consolidation chemotherapy with G-CSF, cladribine, and cytarabine ("G-CLA"), which should begin within 6 weeks of achieving CR/CRi once patients have recovered to \leq Grade 2 toxicities from the previous course of therapy.

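### Sections 3.1.2 and 3.1.4 still make relapsed/refractory patients eligible, and 3.1.7 still allows prior G-CLAM for AML, in a trial now restricted to newly diagnosed patients

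*Combined protocol and SAP*

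**What the plan says.** **The restriction.** Section 1.0, in the rationale for restricting enrolment (2-2018 update), states the decision: "we have elected to restrict this protocol to ND patients and to work on a new protocol for RR patients". The reason given is that relapsed/refractory patients on this protocol showed "an increased rate of delayed blood count recovery (MLFS) over what would be expected" from experience with G-CLAM without decitabine. Other sections carry the same population:

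- Objective 2.1.1 estimates the MTD of decitabine "when used concomitantly with G-CLAM in patients with newly diagnosed AML" and high-risk MDS.
- Objective 2.2.1 evaluates response and survival "in patients with newly-diagnosed AML / high-risk MDS".
- Section 6.0 describes the study as one of "decitabine given concomitantly with G-CLAM chemotherapy in adults with newly diagnosed AML or high-risk MDS".
- Section 8.5 sets the Phase 1 endpoint in newly diagnosed patients and places Phase 2 in the same population.

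**Eligibility.** Section 3.1.2 has two routes in. The second is for patients whose MDS or AML (APL excepted) was diagnosed earlier. It asks for this: "relapsed/refractory disease according to 2003 recommendations of the International Working Group [21], requiring first or subsequent salvage therapy". Section 3.1.4 adds: "Patients with prior autologous or allogeneic hematopoietic cell transplantation (HCT) are eligible if relapse occurs", on condition that graft-versus-host disease is controlled. Section 3.1.7 accepts earlier mitoxantrone- or cladribine-based treatment for MDS or AML and names G-CLAM.

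**Registration.** Section 5.0 says: "The study PI will be responsible for ensuring that all eligibility requirements according to section 3.0 are met".

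**Statistics.** Section 14.2 still runs de-escalation separately by disease status (newly diagnosed, relapsed/refractory) and by randomization group (sequential, concurrent). Section 14.3 carries Phase 1 patients treated at the RP2D into Phase 2 and names neither disease status nor schedule.

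**The concern.** The sections that say whom the trial is for and the section that decides who gets in give opposite answers. Section 3.0 is the operative one, because it is what registration is checked against. The relapsed/refractory population was withdrawn for a safety-related reason, so leaving its entry route open matters more than ordinary leftover wording. Anyone who applies section 3.0 literally, whether the principal investigator or a designee, would find such a patient eligible.

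The same incomplete update shows in 14.2, which still provides for groups that no longer enrol, and in 14.3, which does not spell out the analysis set. Those two points affect clarity rather than safety.

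**Working it through.** The contested point involves no arithmetic, so the first three steps set the texts side by side. The fourth checks that the correction leaves the design alone.

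**1. Is the restriction current text?**

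| Place | Population |
|---|---|
| 1.0, 2-2018 rationale | Newly diagnosed only; a new protocol for relapsed/refractory |
| 2.1.1 and 2.2.1 | Newly diagnosed |
| 6.0 | Newly diagnosed, concomitant decitabine |
| 8.5 | Newly diagnosed in both phases |
| 3.1.2 | Newly diagnosed **or** relapsed/refractory |
| 3.1.4 | Relapse after transplantation admitted |
| 3.1.7 | Prior AML treatment allowed, including G-CLAM |

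The restriction appears in the objectives, treatment plan and endpoints as well as in the update rationale. The conflict is therefore between live sections, not between a change log and the current text.

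**2. Does anything else close the route?** Section 3.2 lists six exclusions: blast crisis of CML, short expected survival from another illness, active infection, hypersensitivity, pregnancy or lactation, and other investigational agents. None concerns relapsed or refractory disease.

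**3. What happens at registration?** Section 5.0 asks whether section 3.0 is met. A patient in first salvage after G-CLAM who meets the remaining criteria satisfies 3.1.2 and 3.1.7 and is caught by nothing in 3.2, so the answer is yes. Section 14.2 still has an arm in which to place that patient.

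**4. Does the correction touch the design?** The inputs are in 14.3: null rate 0.65, alternative 0.80, continue with at least 13 of 19, succeed with at least 31 of 41. With X₁ ~ Bin(19, p) and X₂ ~ Bin(22, p):

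- Early stopping at p = 0.65: P(X₁ ≤ 12) = 0.519 (the plan states 51%).
- P(success) = Σ, over x = 13 to 19, of P(X₁ = x) × P(X₂ ≥ 31 − x).
- At p = 0.65 this is 0.096 (the plan's limit is 10%).
- At p = 0.80 it is 0.800 (the plan states 80%).

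An exact search for the minimax design returns the same sizes and boundaries. The calculation uses one response rate for all 41 patients, which fits a single newly diagnosed cohort. Changing the eligibility wording alters none of its inputs.

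Section 10 is already written for one group: 12 patients at each of two failed levels plus 41 at the third gives 12 + 12 + 41 = 65.

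**The case against.** The best defence is practical. The study is single-center, the restriction is stated in five places, and the principal investigator is responsible for eligibility and the principal investigator or a designee registers each patient. An investigator who knows the 2-2018 decision would probably not enrol a relapsed/refractory patient, and nothing in the documents shows that one was enrolled after it. This stands as a statement about likelihood. It does not remove the contradiction, because it relies on people remembering section 1.0 when section 5.0 sends them to section 3.0.

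Three stronger readings are tempting, and the documents do not support them.

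- **Loss of power.** A reader might infer that relapsed/refractory patients would enter the 19 and 41 and dilute the response rate. Section 8.5 and the Phase 2 rationale in section 1.0 confine Phase 2 to newly diagnosed patients, so on the natural reading they are not counted. The documents give neither a number of such patients nor their MRDneg CR rate on this regimen.
- **An accrual error.** A reader might multiply out the four groups in 14.2 and conclude that the 41 and 65 in section 10 are too small. That assumes that groups closed in section 1.0 must still fill, and it sets a Phase 1 count against totals that include Phase 2. Section 10 is right for the one open group.
- **An undefined primary analysis.** A reader might infer that newly diagnosed patients on the closed sequential schedule could be counted freely. Section 14.2 ties the RP2D to the randomization group, the dose table in 6.3 defines Level 1 as decitabine from day 1 alongside G-CLAM, and 2.1.1 and 6.0 specify concomitant use. Together these point to the concurrent schedule. No sentence says so outright, which justifies a clarification and no more. Section 1.0 saw no clear difference between the schedules, so no direction of bias can be claimed.

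**Conclusion.** The eligibility contradiction is real and must be fixed. Sections 3.1.2 and 3.1.4 admit a population that sections 1.0, 2.1.1, 2.2.1, 6.0 and 8.5 exclude, 3.1.7 still accommodates it, and neither 3.2 nor 5.0 stops it. The consequence is that a withdrawn population could be registered by following the stated rule. No numerical effect on the primary analysis is claimed, and the design in 14.3 is correct as stated.

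The points on 14.2 and 14.3 are clarifications and do not carry that severity. The conclusion rests only on the current text. It assumes nothing about how many relapsed/refractory or sequential-schedule patients were treated, and the documents do not give those numbers for newly diagnosed patients on the sequential schedule.

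**What to change.** **Required.** Reconcile 3.1.2, 3.1.4 and 3.1.7 with the newly diagnosed restriction already adopted. Section 3.1.7 belongs in the same change, because amending only the first two would leave prior G-CLAM for AML as an accepted history.

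**Secondary, and to be made together.**

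- Rewrite 14.2 for the single open group, newly diagnosed patients on concurrent decitabine, consistent with the 41 and 65 in section 10.
- State in 14.3 that the 19 and the 41 are newly diagnosed patients treated at the RP2D on the concurrent schedule, for both the MRDneg CR count and the DLT count.

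These two go together because the group-specific wording in 14.2 is part of what now separates the schedules. Removing it without the new sentence in 14.3 would open a gap that is at present largely closed.

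**Cost.** A wording amendment. The boundaries (13 of 19, 31 of 41), sample size, type I error and power stay as they are. If any newly diagnosed sequential-schedule patients have already been counted, they would have to be replaced. Section 1.0 says the trial ran as a randomized study for its first 10 months, so such patients may exist.

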3.2 Exclusion Criteria

- **3.2.1** Myeloid blast crisis of chronic myeloid leukemia (CML), unless patient is not considered candidate for tyrosine kinase inhibitor treatment.
- **3.2.2** Concomitant illness associated with a likely survival of <1 year.
- **3.2.3** Active systemic fungal, bacterial, viral, or other infection, unless disease is under treatment with anti-microbials and/or controlled or stable (e.g. if specific, effective therapy is not available/feasible or desired [e.g. chronic viral hepatitis, HIV]). Patient needs to be clinically stable as defined as being afebrile and hemodynamically stable for 24-48 hours.
- **3.2.4** Known hypersensitivity to any study drug.
- 3.2.5 Pregnancy or lactation.
- **3.2.6** Patients may not be receiving any other investigational agents.

4.0 EVALUATION AND COUNSELING OF PATIENT

The patient will be completely evaluated with a history, physical examination, diagnostic testing if necessary, and review of outside slides and records if available. The protocol will be discussed thoroughly with the patient and family (if present), with description of all known risks to the patient. Alternative forms of treatment will be presented as objectively as possible, and the risks and hazards of the study explained to the patient. Consent will be obtained using forms approved by the local Institutional Review Board (IRB).

5.0 PROTOCOL REGISTRATION

To register, the attending physician involved in the care of the potential study participant must contact either the Principal Investigator or, in her absence, a PI-designated member of the study team, and fax a copy of the signed consent form and a signed HIPAA authorization form to the study team ([contact]). The study PI will be responsible for ensuring that all eligibility requirements according to section 3.0 are met. To complete the registration process, the Principal Investigator or his or her designee will assign a patient study number and register the patient on the study. A complete, signed study consent and HIPAA consent are required for registration.

6.0 TREATMENT PLAN

This study is a single-center, open-label phase 1/2 study of decitabine given concomitantly with G-CLAM chemotherapy in adults with newly diagnosed AML or high-risk MDS. Since prior studies have suggested that the hypomethylating activity of decitabine plateaus at 20 mg/m²/d [23] and since data from Fred Hutch #2652.00 discussed above show that decitabine can be given safely for 10 days prior to intensive chemotherapy, we will start our trial with 10 days of decitabine at 20 mg/m²/d and will de-escalate the dose based on DLTs. We will use G-CLAM dose established based on data from Fred Hutch #2734.00 described above. Bone marrows will be reassessed upon blood count recovery or between day Days +25 to +35 after start of G-CLAM chemotherapy, whichever occurs first. Patients achieving CR or CR with incomplete neutrophil or platelet count recovery (CRi) after one induction course are eligible for consolidation chemotherapy with G-CSF, cladribine, and cytarabine ("G-CLA"), which should begin within 6 weeks of achieving CR/CRi once patients have recovered to \leq Grade 2 toxicities from the previous course of therapy.

6.1 Baseline/Pre-Treatment Assessment

The following studies should be obtained at baseline before initiation of study therapy to establish trial eligibility and allow patient characterization and disease prognostication:

- 6.1.1 History and physical examination (assessed within 14 days prior to registration).
- 6.1.2 Peripheral blood and/or bone marrow examination with morphologic and flow cytometric assessment, routine cytogenetic analysis, and molecular testing (FLT3/ITD, NPM1, CEBPA) as needed to establish the diagnosis; a bone marrow biopsy should be obtained if spicules are absent from the aspirate sample

(assessed within 2 months of study day 0 as long as no anti-AML therapy has been given in the interim; if anti-AML therapy has been given, disease status should be reassessed subsequent to this therapy and prior to study day 0).

- **6.1.2** Complete blood counts with differential blood count, including immature cells/blasts; platelet count (assessed within 14 days prior to registration).
- **6.1.3** Testing of renal function, bilirubin, and albumin (should be assessed within 14 days prior to registration).
- **6.1.4** MUGA scan or echocardiography, or other appropriate diagnostic modality, to assess left ventricular ejection fraction (LVEF; assessed within 3 months prior to registration).

6.2 Pre-Treatment

At the discretion of the treating physician, allopurinol 300 mg po daily (or equivalent dose adjusted for renal function) may be considered in all patients without known allergies to allopurinol to reduce the risk of tumor lysis. Higher doses of allopurinol are permitted if patients develop tumor lysis syndrome. Patients may receive rasburicase, a recombinant uric acid oxidase, for the prevention and/or treatment of tumor lysis syndrome at the discretion of the treating physician. All patients should be adequately hydrated and receive anti-emetics as necessary.

